9.5.1.3 Methods for estimating required sample size and expected power

The required sample size and expected power calculations were based on the assumptions described above and were carried out separately for each primary outcome (MCM and select pregnancy loss) at the meta-analysis level. Data sources that had at least a 90% probability of having at least 1 event in each exposure group (see [Table 10](#) and [Table 11](#)) were included in the meta-analysis.

The sample size and power calculations were performed using simulations under the assumption that the true RR is 1.0. For both sample size and power calculations, simulations were repeated 1,000 times to get 1,000 simulated 95% CIs for RRs.

The required sample size to achieve 80% power for a one-sided alpha-level of 2.5% at meta-analysis were performed using simulations as detailed below:

1. For a given overall sample size, a proportion of the overall population was assigned to each of the data sources likely to be included in the meta-analysis (proportions are presented in [Table 12](#)).
2. The number of primary outcome events in each exposure group were randomly drawn for each data source from a binomial distribution. In the binomial distribution, the number of trials was set equal to the estimated data source-level sample size and the probability of success was set to equal to the prevalence of the outcome in each exposure group, assuming that the true RR is 1 (no effect of exposure).
3. The estimated data source level log(RRs), their standard errors, and their 95% CIs were computed using a log-link Poisson regression (in place of log-binomial regression which tended to not converge) from the simulated number of events.
4. The data source level log(RRs) and their standard errors were entered in a fixed-effect meta-analysis model where pooled 95% CIs were computed. The inverse-variance method was used for the meta-analysis. The meta-analysis was run using the meta package in R ([97](#)).
5. The steps 2-4 were repeated for 1,000 times, and the proportion (which represents the achieved power) of the 1,000 simulated 95% CI upper bounds that were smaller than the target RR of 2.5 was computed.
6. The overall sample size was varied to range over positive integers for simulations, and the required sample size for this study was identified as the minimum overall sample size necessary to achieve 80% power (as defined in step 5).

The achieved power (proportion of the simulations where the upper bound of the meta-analysis RR was lower than the target RR of 2.5) was estimated based on the anticipated number of primary outcome events in each exposure groups and using simulations where the steps 2-4 (as described above) were repeated 1,000 times to get 1,000 simulated 95% CIs for RRs. The achieved power was calculated as the proportion of the 1,000 simulated 95% CI upper bounds that were smaller than the target RR of 2.5.

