6. MILESTONES

A progress report is planned 12 months after Pharmacovigilance Risk Assessment Committee (PRAC) endorsement of the protocol (currently assumed to be Q4 2023). It will contain a status update of database applications and any relevant amendments pertaining to database applications. Database access may take between 7 to 18 months; therefore, the progress report may not include patient numbers from each data source.

Two interim reports will be submitted at 36 and 72 months after the progress report. The first interim report will contain descriptive analyses relevant to primary and secondary objectives using all available data at the time of the report. In this report, a descriptive summary of the study outcomes will be provided for the overall study population but blinded to exposure status. The second interim report will contain all descriptive and comparative analyses relevant to the primary and secondary objectives, using *all available* data at the time of reporting. Study outcomes will be provided for the exposure categories. Interim report 2 will not include analyses related to exploratory objectives, sensitivity analyses, or meta-analyses.

The final study report is planned for 31 March 2032 and will include all descriptive, comparative, exploratory, sensitivity, and meta-analytic analyses for all the data sources (Table 2).

Assuming an allocation ratio of 1:2 between anifrolumab exposed and unexposed, minimum sample sizes of 210 anifrolumab users for the MCM outcome and 72 anifrolumab users for the select pregnancy loss outcome would be needed to rule out a target threshold RR of 2.5 with 80% power (see Section 9.5.2). Under the assumption of a final study report milestone of 31 March 2032, and an anifrolumab exposure of 10% in moderate-to-severe SLE pregnancies, the total anticipated number of anifrolumab exposed patients in the selected data sources during the study time period is 353 for the MCM outcome and 497 for the select pregnancy loss outcomes. With these numbers the expected power to rule out a RR of 2.5 is $\geq 96\%$ for the primary study outcomes (for more details on sample size estimations, see Section 9.5). These assumptions will be reviewed in each interim report and study milestones will be adjusted if necessary to ensure a sufficient sample size is obtained.

Table 2: Study milestones

Milestone	Planned date ²
Protocol PRAC approval	14 December 2023
Registration in the EU PAS Register	31 March 2024

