9.5.1.1 Assumptions used for the sample size and power calculations

To estimate the number of anifrolumab exposed SLE pregnancies and the expected number of primary study outcome events in data sources that would be eligible for the analysis in this study, the following assumptions were used:

- **A prevalence of 7% for MCM outcome.** Prevalence of MCM in pregnancies in women with moderate-to-severe SLE was estimated based on a literature search. Among moderate/severe SLE patients exposed to belimumab, birth defect prevalence estimates of 5.6% to 21.7% were observed in post hoc summary of clinical studies and a prospective

pregnancy registry, respectively (86) A prevalence of 6.4% of congenital malformations was observed in renal SLE pregnancies (51) These proxy estimates of MCM in moderate-to-severe SLE align with the observed population based prevalence estimates ranging from 7.4% to 13.6% (114) among women diagnosed with SLE (117).

- **A prevalence of 20% for the composite of select pregnancy loss outcomes (composite of spontaneous abortion and stillbirth).** Prevalence of the composite outcome of select pregnancy loss (spontaneous abortion and stillbirth) in moderate-to-severe SLE pregnancies ranged from 15.3% to 30% (51, 81, 86). For the individual outcomes, the prevalence estimates ranged from 1.8% to 3.7% for stillbirths (51, 103, 120), and the prevalence estimate was 16% (12.1% to 19.9%) for spontaneous abortions (103). Based on the intended objective to evaluate embryo-foetal loss, a composite outcome of spontaneous abortion and stillbirth has been used.
- **Proportion of SLE pregnancies occurring in women with moderate-to-severe disease of 50%.** There is limited information on the proportion of SLE pregnancies that occur in women with moderate-to-severe disease. The proportion of moderate-to-severe disease at the time of diagnosis among the general SLE population is estimated to be 50% (66, 80). Literature regarding medication patterns for SLE pregnant women suggests that 40-45% use immunosuppressors and/or biologics, which may be a proxy indicator of moderate/severe disease (12, 67). Thus, in this study, an assumption of 50% was used.

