- **Proportion of unexposed to confirmed teratogenic SLE SOC and/or non-SLE SOC drugs of 80%.** It is estimated that 80% of the SLE pregnancies are not exposed to SLE SOC and non-SLE SOC confirmed teratogenic drugs before conception, with a time period of 5-half-lives of relevant drug (see list of confirmed teratogenic drugs and half-lives in Table 20), or during pregnancy. This estimate is based on the reported use of SLE SOC and/or non-SLE SOC drugs in SLE population (47, 48).
- **Proportion of anifrolumab exposure during the first trimester of pregnancy of 80%.** The majority of the anifrolumab exposed pregnancies are expected to be unplanned and exposed to anifrolumab only in the early stages of the pregnancy, as the current recommendations indicate that anifrolumab should only be used during pregnancy if the benefit outweighs the risk to the foetus (86). We therefore used the assumption that 80% of all anifrolumab exposed pregnancies are exposed to anifrolumab during the first trimester of pregnancy.
- **Proportion of anifrolumab exposed pregnancies in women with moderate-to-severe SLE of 5% and 10%.** Based on market forecasts, uptake of anifrolumab in the general SLE population is expected to grow from 5% within two years of market launch to 20% by 5 years after market launch. Given the uncertainty of how these forecasts apply to SLE women of child-bearing potential and to use in pregnant SLE women, we used a conservative lower bound (5%) and a more realistic midpoint value (10%) for the proportion of pregnancies in women with moderate-to-severe SLE exposed to anifrolumab.

In addition, to estimate the minimum required sample size and the expected power, the following assumptions were used:

- **Non-inferiority margin of RR of 2.5.** The RR of 2.5 was based on previously reported increase in risk of MCM for exposure to a major teratogenic drug (62).

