9.5.2 Required sample size

The required total sample size was estimated as the minimum sample size necessary to achieve 80% power for a one-sided alpha-level of 2.5% at meta-analysis level to rule out a target threshold RR of 2.5 for each primary outcome (MCM and select pregnancy loss outcomes). The minimum sample size per data source was calculated based on the expected percentage that the data source would contribute to the total sample size in the meta-analysis (Table 12).

For MCM analysis, a total number of 630 live and non-live births (210 anifrolumab and 420 comparator) using a matching ratio of 1:2, or 732 live and non-live births (183 anifrolumab and 549 comparator) using a matching ratio of 1:3 would be required to achieve at least 80% power to rule out an RR of 2.5 or greater. For the select adverse pregnancy loss outcomes analysis, a total number of 216 pregnancies (72 anifrolumab and 144 comparator) using a matching ratio of 1:2, or 244 pregnancies (61 anifrolumab and 183 comparator) using a matching ratio of 1:3 would be necessary to achieve at least 80% power to rule out an RR of 2.5 or greater.

Table 12: Data source level sample size percentages and required sample sizes assuming that only USA (Carelon Research), USA (DAPI) and France contribute to the meta-analysis of the primary outcomes.

Data source	Percentage of the total sample size in the data sources for select pregnancy loss outcomes analysis ^a	Required sample size per anifrolumab exposure group for meta-analysis of the select pregnancy loss outcomes		Percentage of the total sample size in the data sources for MCM analysis ^a	Required sample size per anifrolumab exposure group for meta-analysis of MCM	
		1:2 matching ratio	1:3 matching ratio		1:2 matching ratio	1:3 matching ratio
USA (Carelon Research)	35%	25	21	31%	66	57
USA (DAPI)	35%	25	21	35%	73	64
France	30%	22	19	34%	71	62
In Total	100%	72	61	100%	210	183

^a Based on the estimated number of pregnancies in women with moderate/severe SLE eligible for the analysis and exposed to anifrolumab, as shown in Table 10 and Table 11.

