For the comparison of the study sub-cohorts exposed to anifrolumab and unexposed to anifrolumab within the study cohorts (as defined in Section 9.2.2), the association metrics of RRs will be estimated. The RRs will be estimated if there is at least one outcome event observed per exposure group. Both crude and adjusted RRs will be reported and estimated for each relevant study outcome. The crude and adjusted RRs will be estimated before and after PS adjustment, respectively. The adjusted RRs will be reported only if PS adjustment is suitable for the data. The statistical model to be used for the estimation of the crude and adjusted RRs will be the log-binomial regression or the robust, modified Poisson regression as seen appropriate for the study data (13, 18). If covariate balance is not achieved through PS adjustment, additional adjustment by using unbalanced covariates in the outcome regression model will be considered. Additionally, any other potential covariates (or risk factors) that are not included in the PS model but are hypothesised to be associated with the study outcomes may be used as covariates for the statistical models. Further details on the statistical models will be provided in the SAP.

Meta-analysis

In addition to data source level analyses, results will be combined in a meta-analysis. Meta-analysis will be performed only for the adjusted RR estimates of the primary study objectives (MCM and selected pregnancy loss outcomes). The meta-analysis will be performed using effect size estimates from all study countries for which the adjusted RR were estimated.

Prior to conducting the meta-analyses, heterogeneity across the study countries will be assessed using:

- Cochran's Q test (significance level: 0.1). Q is calculated as the weighted sum of squared differences between individual studies and the pooled value across studies.
- The I^2 statistic (0% to 40%: might not be important; 30% to 60%: may represent moderate heterogeneity; 50% to 90%: may represent substantial heterogeneity; 75% to 100%: considerable heterogeneity). I^2 is calculated as follows:

$$I^2 = \left(\frac{Q - df}{Q} \right) \times 100\%$$

where Q is Cochran's statistic and 'df' is its degrees of freedom. The I^2 is a statistic that estimates the percentage of variance in effects attributable to study heterogeneity rather than sampling error.

- The τ^2 statistic

Considerable heterogeneity would indicate that the study results should be interpreted as inconclusive.

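### The required sizes for select pregnancy loss (72 and 61 exposed) rest on Poisson intervals that are too wide for binary data and differ from those planned for the analysis; MCM is barely affected

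*Protocol*

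**What the plan says.** Section 9.5.1.3 sizes the study by simulation, "performed using simulations under the assumption that the true RR is 1.0". Events in each data source and exposure group are binomial draws. The source-level log risk ratios, their standard errors and their 95% intervals are then "computed using a log-link Poisson regression (in place of log-binomial regression which tended to not converge", and are pooled by fixed-effect inverse variance. A run succeeds when the pooled upper bound lies below 2.5.

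Section 9.5.2 presents the result as "the minimum sample size necessary to achieve 80% power for a one-sided alpha-level of 2.5% at meta-analysis level". The exposed numbers are 72 (1:2) and 61 (1:3) for select pregnancy loss, and 210 and 183 for MCM. Section 6 repeats them as "minimum sample sizes of 210 anifrolumab users for the MCM outcome and 72 anifrolumab users for the select pregnancy loss outcome" and says that milestones will be adjusted if the sample looks insufficient. Section 9.4 links a shortfall against the required size to extra data sources or a longer study.

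For the analysis itself, Section 9.7.1 says that the model "will be the log-binomial regression or the robust, modified Poisson regression as seen appropriate for the study data".

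**The concern.** An ordinary Poisson model treats each event count as having variance equal to its mean. A binary outcome has a smaller variance, by the factor 1 − p. Intervals from the model-based Poisson fit are therefore too wide, and the excess grows with the risk: it is modest at 7% and clear at 20%. Robust (modified) Poisson and log-binomial regression do not have this defect, and those are the models planned for the analysis.

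The sizing and the analysis therefore use different intervals, and the one-sided 2.5% label does not describe the interval used for sizing. What is at stake is the accuracy of the required sizes, since they are the yardstick for judging at the interim reports whether the sample suffices.

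**Working it through.** **Inputs, all from the protocol.** Margin: "Non-inferiority margin of RR of 2.5". True risk ratio 1.0. Risks: "A prevalence of 7% for MCM outcome", and 20% for pregnancy loss (Section 9.5.1.1). Allocation 1:2 and 1:3. Three data sources with the Table 12 splits: loss 25/25/22 and 21/21/19; MCM 66/73/71 and 57/64/62. The protocol used 1,000 runs, so the Monte Carlo standard error at 80% power is √(0.8 × 0.2/1000) = 1.3 points.

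**Variance of log RR**, with a events among n exposed and c events among m unexposed:
- model-based Poisson: 1/a + 1/c
- log-binomial or robust Poisson, unadjusted: 1/a − 1/n + 1/c − 1/m

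**Closed-form check.** With A = ((1.96 + 0.8416)/ln 2.5)² = 9.35 and k unexposed per exposed, the exposed number is (1/p)(1 + 1/k)A for plain Poisson and ((1 − p)/p)(1 + 1/k)A for the binomial variance. For loss at 1:2 this gives 5 × 1.5 × 9.35 = 70.1 and 4 × 1.5 × 9.35 = 56.1. The stated 72 sits with the first. Sparse cells within sources push both figures up somewhat, so simulation is needed for exact sizes.

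**Simulation of the protocol's own steps** (300,000 runs per size for the minimum; 2,000,000 runs for power and error). Error is simulated at a true risk ratio of 2.5 with the unexposed at the stated prevalence.

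| | Loss 1:2 | Loss 1:3 | MCM 1:2 | MCM 1:3 |
|---|---|---|---|---|
| Stated exposed number | 72 | 61 | 210 | 183 |
| Minimum, plain Poisson | 70 | 62 | 210 | 186 |
| Minimum, log-binomial/robust | 61 | 55 | 200 | 179 |
| Power at stated size, plain Poisson | 81.8% | 79.3% | 80.2% | 79.2% |
| Power at stated size, log-binomial/robust | 87.6% | 85.6% | 82.4% | 81.2% |
| One-sided error, plain Poisson | 0.69% | 0.46% | 1.60% | 1.23% |
| One-sided error, log-binomial/robust | 2.4% | 1.8% | 2.2% | 1.7% |

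Repeat runs move the log-binomial/robust minimums by about one, hence 61-62, 55-56, about 200 and about 180 in the text.

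Plain Poisson reproduces all four stated sizes. With the planned variance, power at the stated size exceeds 80% by 7.6 and 5.6 points for loss, about 6 and 4 Monte Carlo standard errors. For MCM the excess is 2.4 and 1.2 points, about 2 and 1 standard errors.

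**Large-sample check of the error, loss 1:2 at the margin.** Expected events are 0.5 × 72 = 36 and 0.2 × 144 = 28.8. Plain variance: 1/36 + 1/28.8 = 0.0625. Binomial variance: 0.0625 − 1/72 − 1/144 = 0.0417. The plain standard error is too large by √(0.0625/0.0417) = 1.22, so the effective critical value is 1.96 × 1.22 = 2.40, a one-sided error of about 0.8%. This agrees with the simulated 0.7%.

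**The case against.** Several counter-arguments have force.

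- **The substitution is disclosed and errs on the safe side.** Section 9.5.1.3 names the Poisson model and gives the reason. No power is overstated. Both points stand; what the protocol does not say is that the substitution changes the error rate and the sizes.
- **All four sizes may look wrong.** A reader might infer that none can be obtained with the planned intervals. The documents do not support that. MCM 1:3 fits either variance and MCM 1:2 is marginal. Table 13 is mixed: for MCM at 5% uptake in 2032 its 69% (1:2) matches the robust variance (69.0%, against 66.0% plain), while its 72% (1:3) is nearer plain Poisson (72.7%, against 75.2%). Only the loss sizes separate the methods clearly.
- **The low error is not all due to the Poisson variance.** At the same sizes the planned intervals also fall below 2.5%, at 1.7-2.4%, so much of the MCM shortfall is small-sample behaviour common to both. The error also depends on which group's risk is fixed: with the exposed at the stated prevalence and the unexposed at that figure divided by 2.5, plain Poisson gives about 0.6-1.0% for loss and 0.8-1.2% for MCM.
- **The stated sizes may look too large for the planned analysis.** That is not established. The binomial variance above is for a crude comparison, whereas the meta-analysis pools adjusted risk ratios after propensity score matching or weighting, and a woman may contribute more than one pregnancy. Either feature can inflate the variance, and the protocol gives no figure for it.
- **A borderline final result might seem to turn on the interval chosen.** As a single stratum, 18/72 against 26/144 losses gives an upper bound of 2.53 with plain Poisson and 2.35 with the binomial variance. But Section 9.7.1 already restricts the final model to log-binomial or robust Poisson, so the first bound would not be produced.
- **Planning hardly changes.** Expected exposed pregnancies for loss are 249 or 497, far above 72. For MCM at 5% uptake, the three pooled sources give 51 + 56 + 58 = 165 by 2032, below either target. The one crossing is 62 + 69 + 75 = 206 by 2034, below 210 but above about 200, and Table 13 already credits that scenario with 80% power at 1:2.

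**Conclusion.** The point holds, clearly for select pregnancy loss and only slightly for MCM. The stated combination of 80% power, one-sided 2.5% and 72 or 61 exposed does not hold together for loss: the sizing interval runs at about 0.7% and 0.5%, and the planned intervals reach 80% power with 10-11 (1:2) and 5-6 (1:3) fewer exposed pregnancies. Against the simulated minimums the stated sizes are about 11-18% high for loss (61/55 and 72/61) and 2-5% high for MCM (183/179 and 210/200).

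This is a minor, conservative error with almost no planning consequence. It rests on three assumptions: that the sizing used model-based Poisson standard errors, which the text implies and the loss sizes confirm; that the comparison is unadjusted with independent pregnancies; and that the protocol's prevalences and Table 12 shares hold.

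**What to change.** Rerun step 3 of Section 9.5.1.3 with sandwich or binomial delta-method standard errors, in line with Section 9.7.1, and with more than 1,000 runs so that the minimum is not blurred by simulation error. Restate the required sizes in the Abstract, Section 6, Section 9.5.2 and Table 12 (about 61-62 and 55-56 for loss; about 200 and 180 for MCM), and refresh Table 13 from the same code. Label the sizes as those of an unadjusted analysis, before any variance inflation from propensity score weighting or repeat pregnancies.

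The cost is one rerun and some text edits; data and conduct do not change. The downside is slightly lower targets with no allowance for that inflation, which is why the label matters.

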9.5.2 Required sample size

The required total sample size was estimated as the minimum sample size necessary to achieve 80% power for a one-sided alpha-level of 2.5% at meta-analysis level to rule out a target threshold RR of 2.5 for each primary outcome (MCM and select pregnancy loss outcomes). The minimum sample size per data source was calculated based on the expected percentage that the data source would contribute to the total sample size in the meta-analysis (Table 12).

For MCM analysis, a total number of 630 live and non-live births (210 anifrolumab and 420 comparator) using a matching ratio of 1:2, or 732 live and non-live births (183 anifrolumab and 549 comparator) using a matching ratio of 1:3 would be required to achieve at least 80% power to rule out an RR of 2.5 or greater. For the select adverse pregnancy loss outcomes analysis, a total number of 216 pregnancies (72 anifrolumab and 144 comparator) using a matching ratio of 1:2, or 244 pregnancies (61 anifrolumab and 183 comparator) using a matching ratio of 1:3 would be necessary to achieve at least 80% power to rule out an RR of 2.5 or greater.

Table 12: Data source level sample size percentages and required sample sizes assuming that only USA (Carelon Research), USA (DAPI) and France contribute to the meta-analysis of the primary outcomes.

Data source	Percentage of the total sample size in the data sources for select pregnancy loss outcomes analysis ^a	Required sample size per anifrolumab exposure group for meta-analysis of the select pregnancy loss outcomes		Percentage of the total sample size in the data sources for MCM analysis ^a	Required sample size per anifrolumab exposure group for meta-analysis of MCM	
		1:2 matching ratio	1:3 matching ratio		1:2 matching ratio	1:3 matching ratio
USA (Carelon Research)	35%	25	21	31%	66	57
USA (DAPI)	35%	25	21	35%	73	64
France	30%	22	19	34%	71	62
In Total	100%	72	61	100%	210	183

^a Based on the estimated number of pregnancies in women with moderate/severe SLE eligible for the analysis and exposed to anifrolumab, as shown in Table 10 and Table 11.

